7.1.3.2.1 Blood Collection for Plasma MK-3682 (and metabolites) and MK-8408

Sample collection, storage and shipment instructions for plasma samples will be provided in the operations/laboratory manual.

Pharmacokinetic samples will be collected from all enrolled subjects according to the PK sampling schemes shown in [Table 12](#). Subjects participating in an intensive viral kinetic sub-study will be providing additional PK samples on Days 3 and 7 that are not being collected from the other subjects in the study. The intensive viral kinetic substudy will include the first 10 GT1, 10 GT2, 10 GT3 and up to the first 5 GT4, 5 GT5 and 5 GT6 subjects who consent to participate.

On all PK visits where a pre-dose sample will be collected, the subject must withhold their dose on the day of the PK visit; the dose will be administered at the site after collection of the pre-dose PK sample. For study visits after Visit 2, if there are cases in which a morning visit is not feasible and a subject is seen in the afternoon, the subject should take their study medication in the morning, after an overnight fast, as per their regular schedule (in accordance with [Section 5.2.2 Timing of Dose Administration](#)) and PK samples will still be collected during these afternoon visits.

All PK samples will be used to evaluate not only PK exposures but also to assess the PK/PD and PK/AE relationships of MK-3682 (and metabolites) and MK-8408. The date and time of each PK sample as well as the date and time of the last dose of MK-3682 and MK-8408 prior to the PK sample will be recorded.

When predose PK samples are collected, information regarding meal qualitative fat content and time of the meal consumed within 5 hr before and 2 hr after the subject's last dose of MK-3682 and MK-8408 prior to the PK samples will be recorded; when postdose PK samples are collected, information regarding meal qualitative fat content and time of the meal consumed within 5 hr before and 2 hr after the subject's last dose of MK-3682 and MK-8408, as appropriate, which is administered at the study site will be recorded also. For subjects who may take multiple meals during the time window, only the meal closest to the last dose prior to the PK samples will be recorded.

Table 12 Pharmacokinetic Sampling Timepoints

Visit Number	Study Day/Week	Time Relative to Dose of MK-3682/MK-8408 ^{3,4}	PK Timepoints for Non-Intensive Viral Kinetic Subjects	PK Timepoints for Intensive Viral Kinetic Subjects
2	Day 1	Pre-dose	x	x
4	Day 3	Pre-dose		x
6	Day 7	Pre-dose	x	x
		0.5-, 2-, and 4-hour ⁵ post-dose		x
7	Week 2	Pre-dose	x	x
8	Week 4	Pre-dose	x	x
		0.5- and 2-hour post-dose ⁵	x	x
9	Week 6	Pre-dose	x	x
10	Week 8	Pre-dose	x	x
11	Week 10	Pre-dose	x	x
12	Week 12	Pre-dose	x	x
13 ¹	Week 14	Pre-dose	x	x
14 ¹	Week 16	Pre-dose	x	x
21	HCV/HIV Viral Failure Confirmation Visit ³	NA	x ²	x ²
22	Early Discontinuation Visit ³	NA	x ³	x ³

¹ If the treatment duration is increased to 16 weeks, Visit 13 (Week 14) and Visit 14 (Week 16) PK samples will be collected.
² PK samples and meal information for PK are to be collected at HCV/HIV viral confirmation or early discontinuation visits that occur only during the study treatment period.
³ Time relative to last dose of MK-3682 and MK-8408 must be recorded in the electronic case report form.
⁴ After study Visit 2, if there are cases in which a morning visit is not feasible and a subject is seen in the afternoon, the subject should take their study medication in the morning, after an overnight fast, as per their regular schedule (in accordance with section 5.2.2 Timing of Dose Administration) and PK samples will still be collected during these afternoon visits.
⁵ 0.5 hour samples may be taken ± 5 minutes, 2 hour and 4 hour post-dose samples may be taken ± 15 minutes.
 Note: ~4 mL of blood will be collected at each specified time point for plasma PK assessment of MK-3682 (and metabolites).
 Note: ~4 mL of blood will be collected at each specified time point for plasma PK assessment of MK-8742 or MK-8408.
 Note: The date and time of the PK sample collection for all MK-3682 (and metabolites) and MK-8408 PK samples must be recorded in the electronic case report form.
 Note: At the time of PK sample collection, subjects will be asked to provide information regarding the time/date of the last MK-3682 and MK-8408 dose prior to the PK sample collection. (This can also be obtained by referencing the subject's study medication diary).

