4.2.2.2 Dose Selection for MK-8408

The 60mg dose of MK-8408 was chosen for the MK-3682B FDC regimen based on the available safety, tolerability, and pharmacokinetic data from the single and multiple dose and drug-interaction studies in healthy volunteers and the pharmacokinetic, pharmacodynamic (PD) and safety profiles of MK-8408 in HCV infected subjects. Preliminary pharmacodynamic data from PN003 are available for doses up to 120 mg in HCV GT3 subjects and demonstrate that following once daily fasted dosing of 10, 30, 60, and 120 mg MK-8408 for 5 days, the mean maximum reduction in HCV VL was -2.83, -3.03, -3.35 and -1.75 log₁₀ IU/mL, respectively. The anomalous fall in VL decline at 120 mg dose of MK-8408 was explained by sequencing of the HCV subjects' isolates that revealed that all 3 subjects in this panel had either baseline or treatment-emergent resistance-associated variant viruses. One subject had the resistant variants S62L/Y93H at baseline and following treatment; this subject had a maximal VL reduction of -0.34 log₁₀ IU/mL. One subject had no detectable RAVs at baseline but had both S62L and Y93H emerge during treatment; this subject had a -1.85log₁₀ IU/mL VL reduction. The third subject had A30K at baseline with emergence of Y93H/Y during treatment; this subject had a -3.06log₁₀ IU/mL VL reduction. These VL results demonstrate that 30 mg and 60mg of MK-8408 are associated with a substantial and rapid initial VL decline of GT3, but that MK-8408 may not exhibit full

efficacy against some GT3 RAVs in the setting of monotherapy administration. Following a single dose of 60mg MK-8408 once-daily \times 5 days the mean maximum reduction in HCV VL in GT1a subjects was $-3.86 \log_{10}$ IU/mL, and the mean maximum reduction in HCV VL in GT2b subjects was $-3.62 \log_{10}$ IU/mL. For detailed information, please refer to the MK-8408 IB.

The fit-for-purpose capsule formulation of MK-8408 demonstrates a moderate negative food effect, with a 50% decrease in C24hr when co-administered with a high fat meal. As such, in this study, subjects will be instructed to take study drugs on an empty stomach after an overnight fast, at least 1 hour before the morning meal. Study drugs should be taken with water, but without food. Drug-drug interaction studies with MK-3682 and MK-8408 (MK-3682 PN007 and MK-3682 PN008) demonstrated no clinically significant drug interactions, thus supporting the coadministration of these drugs without need for dose adjustment.

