5.2.2 Timing of Dose Administration

All doses of MK-3682 and MK-8408 should be taken on an empty stomach after an overnight fast, at least 1 hour before the morning meal. Study medications should be taken with water but without food. In addition, subjects should fast overnight prior to reporting to the study site for dosing on Treatment Day 1 (Visit 2) and for all other visits at which a pre-dose PK sample is to be collected. For study visits after Visit 2, if there are cases in which a morning visit is not feasible and a subject is seen in the afternoon, the subject should take their study medication in the morning, after an overnight fast, as per their regular schedule; PK samples will still be collected during these visits.

If a subject misses a dose of MK-3682 or MK-8408 and it is less than 8 hours before the next dose, the missed dose should be skipped and the normal dosing schedule resumed. Subjects should not double the next dose in order to compensate for what has been missed.

If a subject misses a dose of MK-3682 or MK-8408 and it is greater than 8 hours before the next dose, the missed dose should be taken at least 2 hours after last meal and 1 hour before next meal and the normal dosing schedule resumed.

If for any reason MK-3682 or MK-8408 needs to be interrupted, the entire regimen should be interrupted and can be interrupted for up to 3 days. If the interruption lasts for more than 3 days, consult the Sponsor Protocol team.

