8.4.1.2 Pharmacokinetics Endpoints

Additional details are in Section 4.2.3.3.

The primary PK endpoint for MK-3682 (and metabolites) and MK-8408 is C_{trough}.

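### The PK meal record keeps only the meal nearest the dose, so a permitted later meal can erase a pre-dose meal and fasting cannot be fully verified

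*Combined protocol and SAP*

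**What the plan says.** Section 7.1.3.2.1 collects, for the last dose before a PK sample, "meal qualitative fat content and time of the meal consumed within 5 hr before and 2 hr after" that dose. It then adds a tie-down for anyone with more than one meal in that period: "only the meal closest to the last dose prior to the PK samples will be recorded". Closeness is measured in time alone. Nothing distinguishes a meal before the dose from one after it.

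Section 5.2.2 governs eating around a dose. A regular dose "should be taken on an empty stomach after an overnight fast, at least 1 hour before the morning meal". For a dose taken late, "the missed dose should be taken at least 2 hours after last meal and 1 hour before next meal".

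Section 4.2.2.2 gives the reason for fasted dosing: the MK-8408 capsule "demonstrates a moderate negative food effect, with a 50% decrease in C24hr when co-administered with a high fat meal". Section 8.4.1.2 sets the endpoint at stake: "The primary PK endpoint for MK-3682 (and metabolites) and MK-8408 is" Ctrough. Section 4.2.3.3 says the troughs should also help to assess concentrations and compliance if a subject breaks through on treatment.

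The flow chart row for PK meal information (Section 6.0) is the only meal record. The medication diary in Section 7.1.1.8 holds dose dates, times and unit counts, not meals. Section 8.6.3 leaves the PK analysis to a supplementary SAP.

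**The concern.** The meal that can make a dose non-fasted is usually the one before it, and the 5 h look-back appears to be there to catch it. The closest-meal rule works against that purpose. A subject who follows the instruction and eats 1–2 h after the dose puts a compliant meal inside the window, where it competes for the only slot. If that subject also ate some hours before dosing, the earlier meal is the one discarded, and no other form holds it.

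This matters most for the troughs. From Day 7 onward, the dose behind a pre-dose sample is normally the previous day's, taken at home without supervision (Section 5.2). Fasting for that dose is unobserved, so the meal record is the only check on it. A low MK-8408 trough after an unrecorded meal could be read as poor adherence or left as unexplained variability in the PK/PD work.

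**Working it through.** The plan gives no figure to reproduce here, so this is a check of timing.

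**Inputs**
- Window: 5 h before to 2 h after the dose (7.1.3.2.1).
- Permitted post-dose meal: from 1 h after the dose (5.2.2). Inside the window it therefore falls at *s* hours, with 1 ≤ *s* ≤ 2.
- Pre-dose meal: *t* hours before the dose, with 0 < *t* ≤ 5.

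**Rule.** With both meals in the window, the pre-dose meal is lost when *t* > *s*. A tie (*t* = *s*) is not addressed.

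**By timing of the pre-dose meal**
- *t* < 1 h: *s* is at least 1, so the pre-dose meal is always nearer and is kept.
- 1 h < *t* < 2 h: lost only if the later meal is nearer.
- *t* > 2 h: *s* is at most 2, so the pre-dose meal is always lost.

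**Share of the 5 h look-back exposed to loss**, (5 − *s*)/5:

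| *s* (h after dose) | Share |
|---|---|
| 1 | (5 − 1)/5 = 80% |
| 1.5 | (5 − 1.5)/5 = 70% |
| 2 | (5 − 2)/5 = 60% |

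Put the other way, a recorded post-dose meal at *s* hours shows only that nothing was eaten in the *s* hours before the dose. When such a meal is present, the effective look-back is 1–2 h, not 5 h.

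**Illustration under an assumption.** If *t* is uniform on 0–5 h and *s* is uniform on 1–2 h, the bands give losses of 0%, 50% and 100%. The average is (1×0 + 1×0.5 + 3×1)/5 = 0.70, and a simulation of 1,000,000 draws gave 0.700. This is conditional on both meals occurring, and the uniform timing is assumed. It does not estimate how often a meal is lost in the trial.

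**Late missed dose.** Under the rule in 5.2.2, *t* ≥ 2. If the later meal is inside the window, *s* ≤ 2. So *s* ≤ *t*, and the pre-dose meal is lost except at an exact 2 h/2 h tie.

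**The case against.** If only one meal is to be kept, keeping the nearest is defensible. It retains every meal within 1 h before the dose, against any permitted later meal, and those are the cases closest to co-administration, for which the food effect is documented. Loss needs two meals in the window. For a regular dose, the earlier one already departs from the overnight fast. For a late dose, a meal at least 2 h before meets the protocol's own spacing, so losing it hides no breach. The food effect is stated for MK-8408 capsules only, and PK is listed among the other objectives in Section 3.3. All of this stands, and it limits the point to a gap in data capture.

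A reader might go further and infer that fed doses are analysed as fasted and that mean fasted Ctrough is biased low. For example, assuming that 2% to 20% of doses treated as fasted were really fed, each losing 50%, the mean would be 0.02×0.50 = 1% to 0.20×0.50 = 10% too low, and an affected subject's trough would be halved. The documents do not support this. They define no fed/fasted category and leave the PK analysis to a supplementary SAP that is not among them. They give no frequency for such meals. The 50% belongs to a co-administered high-fat meal, while the displaced meals are those eaten more than 1 h earlier, for which no effect is reported.

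The objection does not answer the narrower point. A departure from the overnight fast is something this record should be able to show, and it can be overwritten by a meal that complies with the protocol.

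**Conclusion.** The point holds as a limitation of the meal record. When two meals fall in the window, a permitted meal 1–2 h after the dose displaces any pre-dose meal eaten longer before the dose than the later meal came after it. This needs no assumption beyond the protocol's own window and spacing. The record therefore cannot fully verify fasting for the dose behind a trough sample, and a possible cause of low MK-8408 exposure can be lost to the Ctrough and PK/PD analyses without means of recovery.

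Its frequency and its effect on exposure cannot be determined from the documents. The 70% figure depends on assumed uniform timing, and the 50% fall in C24hr serves only as an upper bound for earlier meals. SVR12 and the other efficacy analyses do not use the meal record. This is a cheap improvement to the PK data, not a threat to the trial's main results.

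**What to change.** In Section 7.1.3.2.1, replace the closest-meal rule. Within the existing window, record both the last meal before and the first meal after the last dose, each with its time and qualitative fat content. In the supplementary SAP, use both meal times as covariates in the PK analysis. This avoids having to choose a fed/fasted cut-off that the documents do not supply, and the unaddressed tie disappears.

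For data already collected, code any dose with only a post-dose meal recorded as *pre-dose meal status unknown*, not as fasted.

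The cost is one extra meal line on the PK eCRF page, a one-sentence protocol change and a short entry in the supplementary SAP. No visits, blood or subjects are added.

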7.1.3.2.2 Intensive Viral Kinetic Sub-Study

A subgroup of the study population will be included in an intensive viral kinetic sub-study. Approximately ten subjects who are GT1-infected (two of whom are cirrhotics), ten GT2, ten GT3 (two of whom are cirrhotics) and up to five subjects each who are GT4, GT5 or GT6-infected, will be asked to participate in order of allocation until we have reached the targeted numbers per genotype. The data from this sub-study will be used to validate the existing viral dynamics model for MK-3682 and MK-8408.

These subjects will have HCV RNA samples collected during Week 1 as shown in [Table 13](#):

Table 13 Intensive Viral Kinetic Week 1 Sampling Timepoints

Visit Number	Study Day	Time Relative to Dose of MK-3682/MK-8408
2 and 3	Starting on Day 1 and completing on Day 2	Pre-dose and 2, 4, 8, 12, 24, and 32 hours post-dose*
4	Day 3	Pre-dose
5	Day 5	Pre-dose
6	Day 7	Pre-dose

*Post-dose samples may be taken ± 15 minutes for each time point.

HCV RNA samples also will be collected at the Week 2, 4, 6, 8, 10 and 12 visits. If the treatment duration is extended to 16 weeks, HCV RNA samples will be collected at the Weeks 14 and 16 visits during treatment.

Sample collection, storage and shipment instructions for plasma samples will be provided in the laboratory manual.

7.1.3.3 HCV Evaluation

The following specimens are to be obtained as part of Efficacy/Pharmacogenetic Measurements:

- Samples for HCV Genotype evaluation must be obtained for inclusion in the study. All baseline samples will be genotyped using the FDA approved Abbott HCV Real Time Genotype II assay which detects HCV genotypes 1a, 1b, 2, 3, 4, 5, and 6 through the use of genotype-specific fluorescent-labeled oligonucleotide probes in a real-time RT-PCR assay. The RT-PCR reaction uses 3 sets of HCV specific amplification primers targeting the conserved 5'UTR (for all genotypes) and NS5B regions from GT1a and 1b. The assay has accuracy of >96% for GT1, 1a, 1b, 2, 3 and 4, 89% for GT5 and 83% for GT6 with 100% specificity in HCV serologically negative plasma samples. Phylogenetic analyses will be performed using sequences for NS3, NS5A and NS5B to ensure accurate assignment of sample genotype/subtype.
- Blood must be drawn from each subject to assess HCV RNA plasma levels at various time points as shown in the study flow chart. HCV RNA in plasma will be measured using a COBAS™ AmpliPrep/COBAS™ Taqman™ HCV Test, v2.0 ® assay with a lower limit of quantification (LLOQ) of 15 IU/mL. Leftover plasma may be used for viral resistance testing if needed. Also, leftover plasma may be used for future biomedical research only if the subject signed for future biomedical consent.
- Blood must be drawn from each subject to assess viral resistance mutation and processed as instructed by the central laboratory manual. Leftover plasma may be used for future biomedical research only if the subject signed for future biomedical consent.

- Protein and metabolites may be measured from blood samples to compare biomarkers measured prior to treatment, to biomarkers measured at several time points during treatment that correlate with subject response to treatment (e.g., sustained viral response).
- Samples collected for genetic analysis are obtained at Day 1. Any leftover DNA may be used for future biomedical research only if the subject signed for future biomedical research consent.

Note: Samples may also be used for future assay development and validation if the subject signed for future biomedical research consent.

7.1.3.4 HIV Evaluation

The following specimens are to be obtained:

- Blood must be drawn from each subject to assess HIV RNA plasma levels at various time points as shown in the study flow chart (Section 6). HIV RNA in plasma will be measured using a COBAS® AmpliPrep/COBAS® TaqMan® HIV-1 Test, version 2.0 assay with a lower limit of quantification of 20 IU/mL.
- Blood must be drawn from each subject at HIV RNA viral failure confirmation visit (in case of potential failure, defined as HIV-1 RNA \geq 200 copies/mL, confirmed on 2 consecutive tests at least 2 weeks apart in subjects compliant with their HIV ART) to assess viral resistance mutations, and processed as instructed by the central laboratory manual. HIV-1 drug resistance will be assessed using the PhenoSense GT™ HIV Assay, and the Genosure Prime Assay.
- Blood must be drawn from each subject to assess immunologic status. CD4+ T-cell counts will be obtained at screening and at various time points as shown in the flow chart.

The following nomenclature will be used when describing HIV RNA levels:

- HIV-1 RNA <LLOQ, Target Not Detected
- HIV-1 RNA <LLOQ, Target Detected
- HIV-1 RNA copies/mL

7.1.3.5 Planned Genetic Analysis Sample Collection

Sample collection, storage and shipment instructions for Planned Genetic Analysis samples will be provided in the laboratory manual.

7.1.3.6 Future Biomedical Research Sample Collection

The following specimens are to be obtained as part of Future Biomedical Research:

- Leftover DNA for future research
- Leftover plasma from HCV RNA for future research

- Leftover plasma from viral resistance and biomarkers for future research

7.1.4 Other Procedures

7.1.4.1 Withdrawal/Discontinuation

Subjects who discontinue/withdraw from treatment prior to completion of the treatment regimen should be encouraged to continue to be followed for all remaining study visits as detailed in Section 7.1.5.4.

When a subject discontinues/withdraws from participation in the trial, all applicable activities scheduled for the final trial visit should be performed at the time of discontinuation. Any adverse events which are present at the time of discontinuation/withdrawal should be followed in accordance with the safety requirements outlined in Section 7.2 - Assessing and Recording Adverse Events.

7.1.4.1.1 Withdrawal From Future Biomedical Research

Subjects may withdraw their consent for Future Biomedical Research and have their specimens and all derivatives destroyed. Subjects may withdraw consent at any time by contacting the principal investigator for the main trial. If medical records for the main trial are still available, the investigator will contact the Sponsor using the designated mailbox PPD [REDACTED], and a form will be provided by the Sponsor to obtain appropriate information to complete specimen withdrawal. Subsequently, the subject's specimens will be removed from the biorepository and be destroyed. A letter will be sent from the Sponsor to the investigator confirming the destruction. It is the responsibility of the investigator to inform the subject of completion of destruction. Any analyses in progress at the time of request for destruction or already performed prior to the request being received by the Sponsor will continue to be used as part of the overall research trial data and results. No new analyses would be generated after the request is received.

In the event that the medical records for the main trial are no longer available (e.g., if the investigator is no longer required by regulatory authorities to retain the main trial records) or the specimens have been completely anonymized, there will no longer be a link between the subject's personal information and their specimens. In this situation, the request for specimen destruction cannot be processed.

7.1.4.2 Subject Blinding/Unblinding

This is an open label trial; there is no blinding for this trial.

7.1.4.3 Domiciling

The subjects who are participating in the Intensive Viral Kinetic sub-study will report to the clinical research unit (CRU) on the morning of Day 1 prior to trial drug administration and will remain either in the unit or in a local facility until completion of the 32-hour blood draw after the first dose of study medication. At the discretion of the investigator, subjects may be requested to remain in the CRU longer.

